8.1 Definitions

8.1.1 Adverse Event (AE):

Any untoward medical occurrence in a patient or clinical investigation subject administered a product and which does not necessarily have to have a causal relationship with this intervention.

8.1.2 Adverse Event of Special Interest (AESI)

An adverse event of special interest (AESI) is an adverse event (serious or non-serious) of scientific and medical concern specific to the Sponsor's product or program, for which ongoing monitoring and rapid communication by the Investigator to the Sponsor may be appropriate. Such events may require further investigation in order to characterize and understand them. AESIs may be added or removed during a study by protocol amendment.

The AESIs are listed below:

- Pregnancy of a female subject entered in a study as well as pregnancy occurring in a female partner of a male subject entered in a study with Sanofi medicinal products or devices;
 - Pregnancy occurring in a female participant entered in the clinical trial or in a female partner of a male participant entered in the clinical trial. It will be qualified as an SAE only if it fulfills one of the seriousness criteria.
 - In the event of pregnancy in a female participant, Sanofi medicinal products or devices should be discontinued.
 - Follow-up of the pregnancy in a female participant or in a female partner of a male participant is mandatory until the outcome has been determined
- Symptomatic overdose (serious or non-serious) associated with Sanofi medicinal products or devices. An overdose (accidental or intentional) associated with the Sanofi medicinal product or devices is an event suspected by the Investigator or spontaneously notified by the participant (not based on systematic drug count) and defined as any dose

administration which, in the Investigators opinion based on clinical judgment, is considered significantly greater than the prescribed dose of insulin.

Of note, asymptomatic overdose has to be reported as a standard AE.

8.1.3 New Safety Finding

Any (other than reportable individual case safety report (ICSR)) safety issue that may require expedited reporting because providing information that may lead to a change in the known riskbenefit balance for the product and as mentioned, but not limited to, in the following regulatory texts: Europe: Good Pharmacovigilance Practices, modules VI and VII; and US: FDA: 21 CFR Parts 312 Investigational New Drug Application- Section 312.32, (c) (1) IND safety reports.

8.1.4 Related Adverse Event, i.e. Adverse Drug Reaction (ADR)

There is a reasonable possibility according to the External Sponsor that the product may have caused the event.

8.1.5 Serious adverse event (SAE)

Any untoward medical occurrence that at any dose:

- Results in death
- Is life threatening, (Note: the term "life-threatening" refers to an event/reaction in which the patient was at risk of death at the time of the event/reaction; it does not refer to an event/ reaction which hypothetically might have caused death if it were more severe)
- Requires inpatient hospitalization or results in prolongation of existing hospitalization
- Results in persistent or significant disability/incapacity
- Is a congenital anomaly/birth defect, or
- Is a medically important event or reaction. Medical and scientific judgment should be exercised in deciding whether other situations should be considered serious, such as important medical events that might not be immediately life-threatening or result in death or hospitalization, but might jeopardize the patient or might require intervention to prevent one of the other outcomes listed in the definition above.

8.1.6 Unexpected related Adverse Event, i.e. Unexpected Adverse Drug Reaction (ADR)

An adverse reaction, the nature or severity of which is not consistent with the applicable product information (e.g., Investigator's Brochure for an unapproved investigational medicinal product or package insert/summary of product characteristics for an approved product). An expected ADR with a fatal outcome should be considered unexpected unless the local/regional product labeling specifically states that the ADR might be associated with a fatal outcome.

8.1.7 Device Deficiencies

All inadequacies related to the identity, quality, durability, reliability, safety or performance of the medical device including malfunctions, use errors, and inadequate labelling.

8.1.8 Unanticipated Serious Adverse Device Effect

Serious adverse device effect which by its nature, incidence, severity or outcome has not been identified in the current version of the risk analysis report, or any other unanticipated serious problem associated with a device that relates to the rights, safety, or welfare of subjects.

8.1.9 Medical Device Reporting reportable event

- An event that user facilities become aware of that reasonably suggests that a device has or may have caused or contributed to a death or serious injury or
- An event that manufacturers or importers become aware of that reasonably suggests that one of their marketed devices:
 - May have caused or contributed to a death or serious injury, or
 - Has malfunctioned and that the device or a similar device marketed by the manufacturer or importer would be likely to cause or contribute to a death or serious injury if the malfunction were to recur.

8.2 Obligations and Responsibilities of the External Sponsor

The External Sponsor shall be responsible for transmitting to Sanofi all AE's occurring with the use of Sanofi medicinal products.

All complaints and adverse events will be managed and reported in compliance with all applicable regulations and included in the final clinical study report.

For the intervention group:

- All AEs, regardless of seriousness or relationship to Sanofi Medicinal product and study medical devices (e.g., MDC app), spanning from the signature of the informed consent form until the end of the study as defined by the protocol for that patient, are to be recorded on the corresponding page(s) or screen(s) of the CRF.
- Any defect in the device or medical device complaint, with AE must be reported within 24 hours in case of potential Adverse Event or Serious Adverse Event or without AEs must be reported within 5 days by the Investigator in order for a product technical complaint to be completed. Appropriate information (e.g., samples, labels, or documents such as pictures or photocopies) related to product identification and product deficiencies may need to be gathered. The investigator will assess whether or not the quality issue has to be reported together with an AE or SAE.
- Whenever possible, diagnosis or single syndrome should be reported instead of symptoms. The Investigator should specify the date of onset, intensity, action taken with respect to Sanofi Medicinal product or Medical Device, corrective treatment/therapy given, additional investigations performed, outcome, and his/her opinion as to whether there is a reasonable possibility that the AE was caused by Sanofi Medicinal product(s), Medical Device or by the study procedure(s).
- The Investigator should take appropriate measures to follow all AEs until clinical recovery is complete and laboratory results have returned to normal, or until progression has been stabilized, or until death, in order to ensure the safety of the patients. This may imply that observations will continue beyond the last planned visit per protocol, and that

additional investigations may be requested by the monitoring team up to as noticed by the Sponsor.

- When treatment is prematurely discontinued, the patient's observations will continue until the end of the study as defined by the protocol for that patient.
- Laboratory, vital signs abnormalities are to be recorded as AEs only if:
 - Symptomatic and/or
 - Requiring either corrective treatment or consultation, and/or
 - Leading to Lantus (U100) or Toujeo (U300) discontinuation or modification of dosing, and/or
 - Fulfilling a seriousness criterion, and/or
 - Defined as an AESI

For the retrospective control group:

The Sponsor will transmit at the time of the analysis and at the latest the time of study report to Sanofi safety signals or conclusions with potential safety impact if any, based on data documented within the EMR.

8.2.1 Reporting Serious Adverse Events

SAEs will be reported as follows:

- SENDING (within 24 hours, preferably by fax or e-mail) the signed and dated corresponding page(s) from the CRF to the representative of the monitoring team whose name, fax number and e-mail address appear in the clinical trial protocol
- ATTACHING a photocopy of all examinations carried out and the dates on which these examinations were performed. Care will be taken to ensure that the patient's identity is protected and the patient's identifiers in the clinical trial will be properly mentioned on any copy of a source document provided to the Sponsor. For laboratory results, the laboratory normal ranges will be included
- All further documentation will be sent to the monitoring team within 24 hours of knowledge of the SAE. In addition, every effort will be made to further document any SAE that is fatal or life threatening within a week (7 days) of the initial notification.

Any SAE brought to the attention of the Investigator at any time after the end of the study for the patient and considered by him/her to be caused by the Sanofi Medicinal product(s)/study medical devices with a reasonable possibility, will be reported to the monitoring team.

8.2.2 Reporting Adverse Events of Special Interest

For AESIs, the Sponsor will inform Sanofi immediately (i.e., within 24 hours), as per SAE notification guidelines described previously

9 DATA SAFETY MONITORING

9.1 Data Safety Monitoring Plan

A data and safety monitoring plan (DSMP) will be implemented by the PI to ensure that the confidentiality of the research data is maintained. The data and safety monitoring plan for the research information will involve quarterly monitoring by the PI of 1) the removal of direct identifiers from information contained within the electronic research database; 2) the security of the database linking the electronic research database linkage codes with subject identifiers; and 3) any conditions that may negatively impact the confidentiality of information contained within the electronic research database. In addition to the DSMP meetings, the research team will hold meetings to discuss the study (e.g., study goals; progress in data collection, coding, and analysis; identification and documentation of adverse events or subject complaints; violations of confidentiality) and address any issues or concerns at that time. The research staff will also submit annual reports to the IRB at the time of annual renewals.

Sharing of data generated by this project is an essential part of our proposed activities and will be carried out in several different ways. We would wish to make our results available both to the community of scientists and health care providers interested in diabetes and ways to support patients in successful diabetes self-management. Specifically, we intend to present at national/international scientific meetings (e.g., the American Diabetes Association's Scientific Sessions), and in peer-reviewed journals (e.g., the DCES). In addition, we will also present our findings to local health care providers to inform best practices of diabetes care.

Data confidentiality will be closely supervised. All paper-based files will be stored in a locked file cabinet with limited access.

9.2 Frequency of Monitoring

The PI will review subject safety data as it is generated. The PI, sub-investigators, and the research staff will meet at least monthly to re-evaluate study goals, subject recruitment, data coding and retention, documentation and identification of adverse events, complaints and confidentiality of subjects. There will be an evaluation of the progress of the research study, including assessments of data quality, timelines, participant recruitment, accrual, and retention. The PI will also review the outcome and adverse event data to determine whether there is any change to the anticipated benefit-to-risk ratio of study participation and whether the study should continue as originally designed or should it be re-evaluated and changed.

10 WITHDRAWAL OF SUBJECTS

Participation in this research is completely voluntary. An individual's decision whether or not to participate in this research, or to later withdraw from it, will not affect his/her current or future medical care at UPMC or the relationship with the University of Pittsburgh. If a participant chooses to withdraw, any information collected about the participant up until the time of withdrawal will be kept, but no additional information will be collected.

Study investigators may choose to remove participants from the study if a participant is advised by their health care provider to discontinue insulin therapy or if a participant is no longer able to act independently to follow study procedures due to such reasons as mental/cognitive incapacity or moved to assisted living.

In addition, a subject may be considered "lost to follow" if they cannot be reached. Every attempt will be made to contact these participants and after 3 failed attempts a certified letter will be sent to the participant.

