2.2.4 Usual Care Group

A retrospective comparative group will be selected from eligible patients who previously were treated at the UPMC Diabetes Outpatient Clinics. This group was chosen for two reasons. First, patients seen at the UPMC Diabetes Specialty Outpatient Clinics have the most robust data available regarding insulin titration, including HbA1c and FBG and, for many patients, BG meter readings. Secondly, this particular group establishes a standard of specialty care against which to compare MDC and will uniquely inform the benefit of this digital tool. We postulate that if MDC produces outcomes, at the very least, equal to those of specialty practice, the likelihood of benefit to PC care is high. Patients in the usual care group will be identified using EMR data accessed through the UPMC Clinical Data Warehouse. As detailed in the Statistical Analysis Plan, propensity score matching will be used to pair intervention and usual care participants.

Study phase			Phase 2 (Maintenance)	
Visits	1	2	3	
Time point	Baseline	3 Months	6 Months	
Visit window		±2 weeks	±4 weeks	
Study Specific Procedures				
Informed Consent	Х			
Eligibility	Х			
MDC Installation and Education	Х	X ¹		
Patient Surveys ³	Х	Х	Х	
Health Care Provider Surveys ⁴	Х	Х	Х	
Reports of Technical Issues		Х	Х	

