2.6 Statistical Analysis

2.6.1 Power and Sample Size Justification

The primary objective of this study is to estimate the difference in HbA1c between the study treatment groups at 3 months. The sample size justification is based on precision estimate (i.e., confidence interval for the HbA1c difference between groups). The expected standard deviation for the 3-months change from baseline in HbA1c is 1.5. With 109 patients in the interventional arm and 109 patients in the retrospective control arm, the treatment effect, expressed as the LS means difference between arms, would be estimated with an expected precision of \pm 0.40. Additionally, this sample size allows for a sufficient number of patients after drop-out, loss to follow-up and/or missing data to enter the maintenance phase (Phase 2) of the study. Based on previous research and experiences with insulin titration, an anticipated 70% of patients (n=76) will enter Phase 2 of the study.

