3.2.2 Usual Care Group

- Adult male and female patients 18 to 75 years old
- HbA1c > 7.5%
- Started on basal insulin in a UPMC Diabetes Outpatient facility within the past three years of study start

• Has blood glucose data available in EMR (At least two HbA1c measurements corresponding to baseline and a subsequent time point after insulin titration) FBG readings)

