The PI will retain the data for the entire period of this study and will retain the specified records and reports for up to seven years at least seven years after final reporting or publication of the study. If the subject and/or legal representative decide to withdraw or be withdrawn from study participation, they may request that the study data and samples be destroyed. Subject names or other directly identifiable information will not appear on any reports, publications, or other disclosures of clinical study outcomes.

8 **REPORTABLE EVENTS**

Each patient will be carefully monitored for adverse events by the investigator.

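### The rules on follow-up after insulin is stopped, and on keeping data from withdrawn patients, conflict; discretionary removal can bias the 3-month HbA1c comparison in an unknown direction

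*Combined protocol and SAP*

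**What the plan says.** On a patient whose insulin is stopped, Section 10 gives investigators a choice: "Study investigators may choose to remove participants from the study if a participant is advised by their health care provider to discontinue insulin therapy". Section 8.2, in its list for the intervention group, gives a requirement: "When treatment is prematurely discontinued, the patient's observations will continue until the end of the study as defined by the protocol for that patient".

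On data already in hand, Section 10 says of a participant who chooses to withdraw that "any information collected about the participant up until the time of withdrawal will be kept, but no additional information will be collected". The end of Section 7, which covers subjects who withdraw and subjects who are withdrawn, says "they may request that the study data and samples be destroyed".

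On the comparator, Section 2.2.4 says: "A retrospective comparative group will be selected from eligible patients who previously were treated at the UPMC Diabetes Outpatient Clinics". To be eligible, a control must have, under Section 3.2.2, "At least two HbA1c measurements corresponding to baseline and a subsequent time point after insulin titration".

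Sections 2.6.1 and 2.6.2 set out the precision-based sample size, the propensity matching and the models. They mention drop-out and missing data only in general terms, with no rate. They name no analysis population and no rule for patients who stop treatment, are removed or withdraw, or for their matched controls.

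**The concern.** Stopping insulin and leaving the study are different events, and a trial needs to know which one ends data collection. Here the first may trigger the second at an investigator's discretion. The study is open label, Section 5.1.1 allows a study investigator also to be a diabetes care provider, and Section 9.2 has the principal investigator reviewing safety data as they arise. Whether a patient is removed may therefore depend on how treatment has gone, which makes the loss potentially informative.

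Controls are past patients identified from the record. They cannot be removed by an investigator after enrolment, and no criterion drops a control who later stopped insulin. Two things are at stake: the primary contrast, change in HbA1c at 3 months, and the hypoglycemia endpoint, because adverse events are recorded only to the end of the study for that patient.

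**Working it through.** **1. The instructions side by side.**

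| Event | One rule | Other rule |
|---|---|---|
| Insulin discontinued (intervention patient) | Section 8.2: observation continues | Section 10: investigator may remove the patient from the study |
| Data held at withdrawal | Section 10: kept | Section 7: destruction may be requested |

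In the first row, a site could follow Section 10 and thereby fail Section 8.2. In the second, an unconditional statement that data are kept leaves nothing for a request to achieve. Section 10's bar on further collection is worded for patients who choose to withdraw. What is collected after removal by an investigator is not stated.

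**2. Whether the analysis section repairs this.** It does not. With no analysis population and no missing-data rule, a removed patient without a 3-month HbA1c has no defined place in the comparison, and nor does the matched control.

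**3. The plan's own precision.** Inputs from Section 2.6.1: 109 patients per arm, and "The expected standard deviation for the 3-months change from baseline in HbA1c is 1.5". The 95% level is from Section 2.6.2.

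Half-width = multiplier × SD × √(2/n), where 1.5 × √(2/109) = 0.2032.
- Normal: 1.96 × 0.2032 = 0.398.
- t with 216 degrees of freedom: 1.971 × 0.2032 = 0.400.

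The stated ±0.40 is reproduced.

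**4. Possible shift in the intervention mean.** The documents give neither a removal rate nor outcomes for removed patients, so both are assumptions: 3 to 11 of 109 removed (about 3% to 10%), with a mean HbA1c change that differs from that of retained patients by 0.5 to 1.5 points, better or worse.

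If removed patients are left out, retained mean minus full mean = (removed/109) × (retained mean − removed mean). The control mean is taken as unchanged.

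| Removed | Assumed difference | Size of shift | Share of 0.40 |
|---|---|---|---|
| 3 | 0.5 | 3/109 × 0.5 = 0.014 | 3% |
| 8 | 1.0 | 8/109 × 1.0 = 0.073 | 18% |
| 11 | 1.5 | 11/109 × 1.5 = 0.151 | 38% |

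The shift favours the app if removed patients would have done worse and counts against it if they would have done better.

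**5. Loss of precision.** If 11 patients and their matched controls are lost, 98 pairs remain: 1.96 × 1.5 × √(2/98) = 0.42. Precision hardly changes. The concern is the shift, which the confidence interval does not reflect.

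**The case against.** Four objections deserve weight.

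- **The insulin clash is only an ambiguity.** The Section 8.2 sentence sits among adverse-event duties, the Section 10 power is permissive, and the end of the study for a given patient could be read as the date of removal. The sentence would then still bind for patients who stop insulin and are not removed. That reading is possible, but it lets the discretionary power override the follow-up rule in exactly the cases that matter. The text needs settling either way.
- **Removal from the study is not stated to mean exclusion from the analysis.** This is correct. The exposure arises because the analysis section is silent.
- **Hypoglycemia is well captured.** Section 2.4.1 uses patient contact, visits, app data and the record, and Section 8.2 records all adverse events from consent. An event that led to removal should already be recorded, so only later events are at risk.
- **The data-destruction conflict carries little statistical weight.** This stands. Section 7 allows a request without saying it is granted, and nothing links requests to outcome.

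A reader might infer three stronger claims that the documents do not support.

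- **That the bias favours the app.** No section says why insulin would be stopped or that these patients have worse HbA1c. Patients stopped for hypoglycemia, or because insulin is no longer needed, could have better values.
- **That removal is decided with the primary outcome known.** A removal before month 3 precedes the 3-month HbA1c.
- **That outcomes can be lost from the intervention arm alone.** Controls without a follow-up HbA1c are never selected, so the asymmetry concerns discretionary removal after enrolment and not all missing data.

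**Conclusion.** Both conflicts are in the current text. The one that matters for the analysis is between Sections 8.2 and 10. Combined with the silence of Section 2.6, it allows 3- and 6-month HbA1c and later safety data to be lost through a discretionary act that has no counterpart among the controls. The result can be bias in the primary comparison; its direction cannot be determined from the documents and its occurrence is not shown.

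The illustrative size is 0.01 to 0.15 HbA1c points in either direction, at most a little over a third of the stated ±0.40. It rests wholly on the assumed removal rate and outcome difference and on removed patients being left out of the analysis. The realistic effect may be small, but data not collected, or destroyed, cannot be recovered later. The conflict between Sections 7 and 10 is mainly a matter of consistent wording.

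**What to change.** Reconcile Sections 7, 8.2 and 10, and add the matching rule to Section 2.6.2:

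- Discontinuing insulin or the app ends neither data follow-up nor inclusion in the analysis.
- The 3- and 6-month HbA1c and safety data continue to be abstracted from the medical record unless the patient withdraws consent for data use.
- These patients are analysed in the intervention group.
- One rule applies to data already collected at withdrawal, in the same terms in the protocol and the consent form.

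The cost is protocol and consent wording plus a little more record abstraction. HbA1c is already taken from clinical records, so no extra visits are needed. Keeping these patients in defines the effect regardless of discontinuation, and the plan should say so. This takes no position on when insulin should be stopped.
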